To avoid biased reporting, patients must not be told the number of headache days or migraine headache days on which study qualification is based.

Study Period III: At the start of the 3-month double-blind treatment phase (Visit 3), patients meeting all eligibility requirements will be randomized to 1 of 3 treatment groups in a 2:1:1 ratio to receive placebo, 120 mg/month LY2951742, or 240 mg/month LY2951742, respectively. At Visit 3, if available and where local regulations and Ethical Review Boards allow, patients will also watch a training video designed to address patient expectations with regard to participation in a placebo-controlled trial and the difference between medical treatment and research. To preserve blinding throughout the study, patients in all treatment groups will receive 2 injections of investigational product at each dosing visit (two placebo injections, two 120-mg LY2951742 injections, or one placebo injection and one 120-mg injection). Patients randomised to the 120-mg dose of LY2951742 will receive an initial loading dose of 240 mg (2 injections of 120 mg each).

The patient will be considered enrolled in the study when randomization occurs. During this phase, study procedures at dosing visits must always occur prior to the patient receiving their assigned treatment.

Patients will be given investigational product (LY2951742 or placebo) injections during office visits (Figure CGAI.1). For all treatment groups, investigational product is administered by subcutaneous injection once monthly at the dosing visits. At Visit 3 (first dose), patients are required to remain in the office for observation for 30 minutes post injection. Patients will continue to log in and complete the ePRO diary each day. Patients may continue to take their allowed acute migraine headache medication (with some limitations; see Section 6.8) during the treatment phase.

Patients will receive their last double-blind dose of investigational product at Visit 6. Patients who do not opt to continue into Study Period IV will receive no further injections and will proceed directly to the post-treatment follow-up phase.

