6.9.2. Continued Access

Investigational product will not be made available to patients after conclusion of this study.

7. Discontinuation Criteria

Patients who discontinue the study or investigational product during the double-blind treatment phase (Study Period III) or open-label treatment (Study Period IV) will proceed immediately to Study Period V.

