- Time to initiation of treatment with a migraine preventive medication (in days) in the post-treatment phase is defined as the disposition date of the previous study period before entering SP V minus the date of start of the migraine preventive medication (based on information collected from concomitant medication e lectronic case report form [eCRF]) in the post-treatment phase. If a patient did not initiate preventive treatment during SP V, they will be censored at the disposition date of SP V. This analysis will be conducted only for patients who entered SP V and those who are not in concurrent preventive treatment group.
- Number of migraine headache days with nausea and/or vomiting is calculated as the total number of migraine headache days with an answer of "yes" to Question 8 in a 30-day period.
- Number of migraine headache days with photophobia and phonophobia is calculated as the total number of migraine headache days with an answer of "yes" to Question 7 in a 30-day period.
- Number of migraine headache days with aura is calculated as the total number of migraine headache days with an answer of "yes" to Question 12 in a 30-day period.
- Number of migraine headache days with prodrome symptoms other than aura is calculated as the total number of migraine headache days with an answer of "yes" to Question 13 in a 30-day period.
- Number of non-migraine headache days with aura is calculated as the total number of non-migraine headache days with an answer of "yes" to Question 12 in a 30-day period.
- **Proportion of aura among migraine attacks** is calculated as follows: 1) among all the migraine attacks, only if aura happened on the first day of migraine attack, it will be counted as migraine attack with aura, 2) then within each period, proportion of aura among migraine attacks is calculated as the total number of migraine attacks with aura divided by total number of migraine attacks.
- Number of days with abortive medication use is calculated as the number of calendar days in a 30-day period on which abortive medication is used.
- Number of classes of abortive medications used is calculated as the total number of classes of abortive medications taken during a 30-day period.

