5.5.1.5. Baseline and Postbaseline Definition

Table CGAI.5.4 describes the rules for determining the patient population and baseline and postbaseline observations for each study phase and type of analysis. When "last of Visit x-x" is used in the table, the last nonmissing observation obtained in the visit interval will be used.

Table CGAI.5.4. Patient Population with Baseline and Postbaseline Definitions by Study Period and Type of Analysis

Study Period / Analysis	Patient Population	Baseline Observation	Postbaseline Observation(s)
Study Period III			
Efficacy analyses (Repeated Measures) or average of observed monthly values	ITT Population with a baseline and at least 1 postbaseline observation	Visit 3	All scheduled visits 3 < Visits ≤7
Efficacy analyses at LOCF endpoint		Visit 3	Last of Visit 3.01-7
Quality of Life analyses (Repeated Measures)		Visit 3	All scheduled visits 3 < Visits ≤7
Quality of Life analyses at LOCF endpoint or for average of observed monthly values		Visit 3	Last of Visit 3.01-7
TEAEs	Safety Population	All Visits 1–3	All Visits 3.01–7
Serious Adverse Events, Discontinuations due to Adverse Events	Safety Population	NA	All Visits 3.01–7
C-SSRS categorical analyses	Patients with a baseline and at least 1 postbaseline C-SSRS assessment	Recent History: Visits 1–3 excluding lifetime ^a All Prior History: Visits 1–3 including lifetime ^a	All Visits 3.01–7
Treatment-emergent abnormal laboratory values	Safety Population with normal laboratory values at all nonmissing baseline visits (with respect to direction being analyzed) and who have at least 1 postbaseline observation	Low: Minimum from Visits 1–3 High: Maximum from Visits 1–3 Abnormal: All Visits 1–3	Low: Minimum from Visits 3.01–7 High: Maximum from Visits 3.01–7 Abnormal: All Visits 1–3
Treatment-emergent immunogenicity	Safety Population	Visit 3	All Visits 3.01–7
Treatment-emergent changes in temperature and weight	Safety Population with a baseline and at least 1 postbaseline observation	Low: Minimum from Visits 1–3 High: Maximum from Visits 1–3	Low: Minimum from Visits 3.01–7 High: Maximum from Visits 3.01–7
Treatment-emergent changes in blood pressures, pulse, and ECGs	Safety Population with a baseline and at least 1 postbaseline observation	Low: Last non-missing from Visits 1–3 High: Last non-missing from Visits 1–3	Low: Minimum from Visits 3.01–7 High: Maximum from Visits 3.01–7

Patient Population with Baseline and Postbaseline Definitions by Study Period and Type of Analysis

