5.5.5. Exposure to Investigational Medicinal Product

Patients will receive the investigational medicinal product (IMP) at the following planned time points:

- Beginning of Month 1 (Visit 3)
- Beginning of each month from Month 2 to Month 11 (Visit 5 to Visit 15)

The following information will be recorded on the eCRF for each dose:

• Confirmation that the patient received the IMP (including reason if the IMP was not given)

• Date and time of administration

The following will be derived from the information recorded on the eCRF:

- For double-blind treatment phase (SP III), duration of exposure in days is calculated as treatment phase disposition date – first date IMP administered +1
- For open label phase (SP IV), duration of exposure in days is calculated as open label disposition date first date IMP administered during SP IV +1.
- For double-blind treatment phase (SP III), number and percentage of patients with 1 dose, 2 doses, and 3 doses injected.
- For open label phase (SP IV), number and percentage of patients with 1 dose, 2 doses, 3 doses,, 8 doses, and 9 doses injected.

Comparisons between treatments for duration of IMP exposure will be performed using an ANOVA with treatment, baseline medication overuse (yes versus no) and concurrent prophylaxis (yes versus no) in the model. The number of patients with 1 dose, 2 doses, 3 doses, 4 doses, 5 doses, 6 doses, 7 doses, 8 doses, ..., 12 doses injected will be summarized. The number of patients with 1 dose, 2 doses, and 3 doses will be compared between treatment groups with CMH test. In addition, injections not administered with the corresponding reasons will be listed.

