The number of weekly migraine headache days in Month 1 can be considered as ordinal data with possible values of 0, 1, 2, 3, 4, and etc. and it will be analyzed using an ordinal repeated measures model implemented using the GLIMMIX procedure in SAS. In this model, a proportional odds model with cumulative logit link will be used, and a random intercept will be applied to the observations for each patient to account for repeated measures. The model will include the fixed, categorical effects of treatment, pooled country, baseline medication overuse, concurrent prophylaxis use, week, and treatment-by-week interaction, as well as the continuous, fixed covariate of baseline number of migraine headache days, and baseline number of migraine headache days-by-week interaction. Log (number of compliant calendar days within each week/7) will be included as the offset in the model.

Time to Event Measures

For the following time to event measures, a Kaplan-Meier curve of the time to event and treatment group comparison using stratified log-rank test stratifying for pooled country, baseline medication overuse and concurrent prophylaxis use will be provided.

- Time to first 50% response in SP III for ITT population.
- Time to first loss of 50% response in SP V for patients who met 50% response criteria at their last injection interval and also entered SP V.
- Time to initiation of preventative treatment for migraine or probable migraine in SP V for patients who entered SP V and those who are not on concurrent preventive treatment group.

Distribution of Response Rate

Overall x% response rate during the double-blind treatment phase will be estimated for X=0, 5, 10, ..., 95, and 100, using GLIMMIX model as described earlier in this section. These estimated response rates will be plotted and points within each treatment arm will be connected to show a curve of response rates. No statistical comparisons will be conducted among different treatment arms.

Analysis for PGI-I

When analyzing PGI-I, baseline PGI-S score will be included as a covariate. Specifically, it will be analyzed with an MMRM analysis while the covariates include the fixed categorical effects of treatment, month, pooled country, baseline medication overuse (yes versus no), concurrent prophylaxis use (yes versus no) and treatment-by-month interaction, as well as the continuous fixed covariates of baseline PGI-S score and baseline PGI-S score-by-month interaction.

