Average pain score for non-migraine chronic pain assessment	ANCOVA*a	MMRM for SP III/IV	
Among patients previously treated with LY2951742 who met 50% response criteria at Month 3 in the double-blind treatment period, the proportion of patients who demonstrate 50% response for at least 6 of the 9 months in the open-label treatment period	N/A	Logistic regression for SP IV	
X% response rate (X=30, 50, 75, or 100) (visit wise)	GLIMMIX	GLIMMIX for SP III/IV and SP III/IV/V	
Distribution of response rate in SP III	GLIMMIX (to get estimated response rates)	N/A	
50% response sustained from month 1 to month 3	Logistic Regression	N/A	
Time to first 50% response in SP III	Kaplan-Meier curve and stratified log-rank test	N/A	
Time from the end of SP IV to no longer meeting 50% response		Kanlan Majar aurus	
criterion	N/A	Kaplan-Meier curve	
Time from the end of SP IV to start use of preventative treatment for migraine	11//1	and stratified log- rank test for SP V	

[figure not shown]
Abbreviations: ANCOVA = analysis of covariance; GLIMMIX = Generalized linear mixed model (for binary variables); MMRM = Mixed models repeated measures; N/A= Not applicable.

^{*}a For PGI-S, ANCOVA with LOCF endpoint will be conducted; for all the other measures, ANCOVA with average monthly measures during 3 month treatment phase will be conducted.

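### SAP subtracts time to preventive medication in Study Period V backwards, and the Study Period III window for abnormal laboratory values repeats the baseline visits

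*SAP*

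**What the plan says.** **Time to preventive medication.** SAP section 5.4.1 defines this SP V endpoint, in days, as "the disposition date of the previous study period before entering SP V minus the date of start of the migraine preventive medication". For patients who start no preventive in SP V it says "they will be censored at the disposition date of SP V". It gives no separate formula for the censored time.

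Section 5.5.10.3 lists "Time to initiation of preventative treatment for migraine or probable migraine in SP V" among the measures to be shown as a Kaplan-Meier curve and compared by a log-rank test stratified for pooled country, baseline medication overuse and concurrent prophylaxis. In the same section, Table CGAI.5.5 describes the variable as "Time from the end of SP IV to start use of preventative treatment for migraine".

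Patients can reach SP V without passing through SP IV. Protocol section 4.1 says that those who do not opt into the open-label phase "will receive no further injections and will proceed directly to the post-treatment follow-up phase". Protocol section 7 says that those who discontinue in SP III or SP IV "will proceed immediately to Study Period V".

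For comparison, SAP section 5.5.5 computes double-blind exposure as "treatment phase disposition date – first date IMP administered +1", that is, later date minus earlier date.

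**Laboratory window.** In Table CGAI.5.4, the SP III row for treatment-emergent abnormal laboratory values ends its postbaseline column with "High: Maximum from Visits 3.01–7 Abnormal: All Visits 1–3". The baseline column of that row also gives Visits 1–3 for abnormal values. The matching SP IV row uses Visits 7.01–16 for low, high and abnormal alike. Section 5.5.12 refers to this table for the baseline and postbaseline of all safety measures, subject to exceptions stated elsewhere. Section 5.5.12.1.5 restricts the analysis of normal/abnormal analytes to patients whose baseline values are all normal, and counts an abnormal value at any later visit.

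**The concern.** Both are operative derivation rules, and both give a wrong result if programmed as written.

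The first concerns a listed other secondary endpoint with an inferential comparison. A time-to-event analysis needs durations that increase with time since the origin, and the written subtraction produces the opposite. Reversing the sign does not settle the definition, because the SAP names two origins and one of them is missing for some patients.

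The second concerns safety results from the placebo-controlled period. An incidence of zero in every arm could be read as a clean finding when the rule had excluded every possible case. Section 5.8.1.2 makes the analyses at the second interim the final double-blind results for the study report, so no later analysis is planned that would replace them.

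**Working it through.** The plan states no figure to reproduce. The check applies each rule literally and then as corrected.

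**1. Time to preventive medication**

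Inputs:
- Origin: disposition date of the period before SP V, set to day 0 (SAP 5.4.1).
- Event: start of a preventive on day *t* ≥ 0, because only starts within SP V count (SAP 5.4.1).
- Scheduled length of SP V: two intervals of 60 ± 5 days (Protocol Appendix 2), so 2 × 55 = 110 to 2 × 65 = 130 days, nominally 2 × 60 = 120.

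Formulas: as written, 0 − *t* = −*t*. Corrected, *t* − 0 = *t*, or *t* + 1 with the day-count convention of section 5.5.5.

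| Start day | As written | Corrected | Corrected, +1 |
|---|---|---|---|
| 0 | 0 | 0 | 1 |
| 31 | −31 | 31 | 32 |
| 45 | −45 | 45 | 46 |
| 90 | −90 | 90 | 91 |
| 120 | −120 | 120 | 121 |

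Over the scheduled length, values run from 0 to −130 as written and from 0 to 130 when corrected. The order also reverses: the day-120 starter (−120) sorts before the day-31 starter (−31).

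A made-up example of 10 patients shows the effect. Events are at days 35, 50 and 90; censoring is at days 40, 60, 70, 118, 120, 121 and 122, counted forwards.
- Corrected: 9/10 = 0.90 at day 35; 0.90 × 7/8 = 0.7875 at day 50; 0.7875 × 4/5 = 0.63 at day 90.
- As written, negative times kept: the events fall at −90, −50 and −35, all before any censoring. Survival is 9/10 = 0.90, then 0.90 × 8/9 = 0.80, then 0.80 × 7/8 = 0.70.
- As written, negative times dropped: no events remain.

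The +1 must apply to both kinds of time or to neither. If it applied to events only, a start on day 120 would be recorded as 121 and a patient censored that same day as 120.

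**2. Laboratory window**

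Inputs: haematology, chemistry and urinalysis are scheduled at Visits 1, 3 and 7 up to the end of SP III (Protocol Appendix 2). Eligibility requires normal values at all of Visits 1–3 (SAP 5.5.12.1.5 with Table CGAI.5.4).

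- Written postbaseline window, Visits 1–3: contains scheduled Visits 1 and 3. Every eligible patient is normal at both, so the count is 0.
- Window used for low and high, Visits 3.01–7: contains scheduled Visit 7. A patient normal at Visits 1 and 3 and abnormal at Visit 7 counts under this window and does not count under the written one.

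The written window therefore takes in both scheduled baseline samples and none of the single scheduled postbaseline sample.

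**The case against.** The best counter-argument is that these are slips of wording whose meaning is plain. Section 5.4.1 calls the variable a time in days, Table CGAI.5.5 states it forwards, and negative durations would show at the first program run. The endpoint has no multiplicity control. Section 5.4.1 also supplies both ends of the censored interval, even without a formula. All of this is fair and limits the weight of the point. It does not make the written rule usable, and the choice between the two origins still has to be made.

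On the laboratory window, the table applies only where nothing else is specified, and section 5.5.12.1.5 asks for an abnormal value that follows baseline. A value from Visits 1–3 cannot follow a baseline made up of those visits. That shows the intent, but the section gives no visit numbers to replace the table entry. The documents also do not list which analytes are classed only as normal or abnormal. They may be few, so the sampling schedule does not measure how many results are affected.

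Three further objections stand in part. The +1 is a matter of choice. The 130-day limit assumes visits on schedule. The adjacent row of Table CGAI.5.5, on loss of 50% response, uses the same end-of-SP-IV shorthand although section 5.4.1 starts that clock at the beginning of the post-treatment phase, so it should be aligned as well.

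**Conclusion.** Both definitions are wrong as written and should be corrected.

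For the SP V endpoint, the sign error needs only that the start date is on or after the preceding period's disposition date, which the definition itself requires. It does not depend on the assumed length of SP V. Whether the analysis would then reverse the ranking or lose its events depends on how negative times are handled, which the SAP does not say.

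For the laboratory rule, SP III incidence is 0% by construction in every arm for normal/abnormal analytes if the table entry is followed. The low and high analyses and the hepatic threshold summaries are unaffected.

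Neither error touches the primary or key secondary analyses. This is a correction of definitions, not a flaw in the design.

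**What to change.** - **SAP 5.4.1:** define event time as the preventive start date minus the disposition date of the study period preceding SP V, and censoring time as the SP V disposition date minus that same date. Add 1 to both or to neither. Adding 1 to both matches the exposure formula in section 5.5.5 and gives a same-day start a time of 1 instead of 0.
- **Table CGAI.5.5:** replace the end of SP IV as origin of this endpoint with the disposition date of the period preceding SP V, so that patients entering from SP III are covered. Align the neighbouring loss-of-response row with its own definition in 5.4.1 in the same edit.
- **Table CGAI.5.4:** change the SP III postbaseline entry for abnormal values to all Visits 3.01–7.

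The cost is three short text corrections. No new data are needed, and the design, the primary analysis and the key secondary analyses do not change.

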- [27] Evidence of significant active or unstable psychiatric disease by medical history, such as bipolar disorder, schizophrenia, personality disorders, or other serious mood or anxiety disorders. Note: Patients with major depressive disorder or generalized anxiety disorder whose disease state is considered stable and expected to remain stable throughout the course of the study, in the opinion of the investigator, may be considered for inclusion if they are not on excluded medications.
- [28] Patients who, in the clinician's judgment, are actively suicidal and therefore deemed to be at significant risk for suicide, or those who have answered "yes" to either Question 4 (Active Suicidal Ideation with Some Intent to Act, Without Specific Plan) or Question 5 (Active Suicidal Ideation with Specific Plan and Intent) on the "Suicidal Ideation" portion of the Columbia Suicide Severity Rating Scale (C–SSRS), or answer "yes" to any of the suicide-related behaviors (actual attempt, interrupted attempt, aborted attempt, preparatory act or behavior) on the "Suicidal Behavior" portion of the C–SSRS; and the ideation or behavior occurred within the past month.
- [29] Women who are pregnant or nursing.
- [30] Patients who have used opioids or barbiturate containing analgesic >3X per month for the treatment of pain in more than 2 of the past 6 months (opioid administration in an emergency setting may be an exception).
- [31] History of drug or alcohol abuse/dependence within 1 year prior to Visit 1 (excessive or compulsive use as judged by the Investigator), or currently using drugs of abuse (including opioids, barbiturates and marijuana), or any prescribed or over-the-counter medication in a manner that the Investigator considers indicative of abuse/dependence.

- [32] Have a positive urine drug screen for any substances of abuse at Visit 1. Note: A retest is allowed if the urine drug screen is positive for any prescribed substance or if, in the judgment of the investigator, there is an acceptable explanation for the positive result. The results of the retest must be negative at or prior to Visit 2.

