6.8. Concomitant Therapy

Table CGAI.3 contains the list of medications that are, and are not, allowed in this study. The concomitant use of acute medications to treat migraine is allowed, with some limitations. In general, treatments used for the prevention of migraine are not allowed at any time during Study Periods I through IV. However, the study will allow approximately one-third of enrolled patients to continue migraine prophylactic treatment with either topiramate or propranolol if the patient has been on a stable dose for at least 2 months prior to Visit 2 and if dosing will remain stable throughout the double-blind treatment period.

Table CGAI.3. Treatments Allowed and Treatments Not Allowed as Concomitant Therapy

Medications allowed for the ACUTE treatment of migraine headaches or other pain or injury:

Acetaminophen (paracetamol), NSAIDs; Triptans; Ergotamine and derivatives; Isometheptene mucate, dichloralphenazone and acetaminophen combination (Midrin); or combinations thereof.

The following medications are allowed with restrictions:

- 1. Opioid and barbiturates no more than 3 days/month (SP II, III and IV).
- 2. Single dose of injectable steroids allowed only once during the study, in an emergency setting (SP III and IV).

Table CGAI.3. Treatments Allowed and Treatments Not Allowed as Concomitant Therapy (continued)

Medications, Procedures or Devices not allowed for any reason/indication:

Acetazolamide

Acupuncture

Anticonvulsants/Antiepileptics (except topiramate if per protocol Section 6.8)

Antipsychotics

Beta-blockers (except propranolol if per protocol Section 6.8)

Botulinum toxin applied to head/neck area

Cannabis / Cannabinoids

Chiropractic procedures, physiotherapy, TENS or other electric devices on head and neck

Corticosteroids for oral use

Flunarizine

Herbals with anti-inflammatory effect (feverfew, willow bark, petasites/butterbur), herbals with sympathomimetic effect (ma huang, ephedra, bitter orange, synephrine) and herbals with catecholamine transmitter reuptake inhibition (St John's Wort)

Monoamine oxidase inhibitors (MAOIs)

Memantine

Serotonin 5HT2a/2c antagonists, e.g.: trazodone, nefazodone

Stimulants (prescription strength), e.g.: methylphenidate, dextroamphetamine, mixed amphetamine salts

Tizanidine

Therapeutic antibodies, e.g.: adalimumab, infliximab, trastuzumab, bevacizumab, etanercept, etc.

Tricyclic antidepressants (TCAs)

Triptans for prophylaxis of menstrual related migraine

Venlafaxine

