For a patient who discontinues early in the double-blind (Study Period III [SP III]) or open-label treatment phase (Study Period IV [SP IV]) or post-treatment phase (SP V), compliance rate for the last month of that study period will be calculated with a denominator of 30 days (or the actual number of days in the interval if greater than 30).

For the rest of months and patients, the compliance rate will be calculated as described in Section 5.5.7.

Other Secondary and Exploratory Efficacy Measures

The same approach for adjusting the number of days within each period to a 30-day period and the same approach to imputing monthly data based on compliance as for the primary measure will be applied to all efficacy measures that are derived from ePRO diary data and need normalization to 30-day period, including:

- Number of ICHD migraine headache days is calculated as the number of calendar days in a 30-day period on which a migraine occurs. Probable migraine is excluded.
- **Number of headache days** is calculated as the number of calendar days in a 30-day period on which a headache occurs.
- Number of moderate-severe headache days is calculated as the number of calendar days in a 30-day period on which a headache occurs with a moderate or severe severity.
- **Number of headache hours** is calculated as the total number of headache hours in a 30-day period on which a headache occurred.
- **Number of migraine headache hours** is calculated as the total number of headache hours in a 30-day period on days when a migraine or probable migraine occurs.
- Number of migraine headache days with medication use is calculated as the number of calendar days in a 30-day period on which migraine or probable migraine occurs and abortive medication is used.

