Abortive medication use will be classified into the following 5 classes: triptans, nonsteroidal anti-inflammatory drugs (NSAIDs)/aspirin, acetaminophen/paracetamol, ergots, anti-nausea. If Question 10 in patient diary questionnaire has an answer of "No", any abortive medication entered for that date will not be included in the analyses.

- Number of classes of abortive medications used on migraine headache days is calculated as the total number of classes of abortive medications taken on migraine headache days during a 30-day period.
- Average number of classes of abortive medications used per day is calculated as follows for each period:

$$\frac{\sum_{i=1}^5 i*n_i}{\sum_{i=0}^5 n_i}$$

Where n_i denotes the number of days during a period with i class(es) of abortive medication use, and i = 0,1,...,5.

• Average number of classes of abortive medications used per migraine headache day is calculated as follows for each period:

$$\frac{\sum_{i=1}^{5} i * m_i}{\sum_{i=0}^{5} m_i}$$

Where m_i denotes the number of migraine headache days during a period with i class(es) of abortive medication use, and i = 0,1,...,5.

- **Number of days with triptan use** is calculated as the number of days with triptan use during a 30-day period.
- Number of migraine headache days with triptan use is calculated as the number of migraine headache days with triptan use during a 30-day period.
- Number of days with NSAIDs/aspirin use is calculated as the number of calendar days with NSAIDs/aspirin use during a 30-day period.
- Number of migraine headache days with NSAIDs/aspirin use is calculated as the number of migraine headache days with NSAIDs/aspirin use during a 30-day period.
- Number of days with acetaminophen/paracetamol use is calculated as the number of days with acetaminophen/paracetamol use during a 30-day period.
- Number of migraine headache days with acetaminophen/paracetamol use is calculated as the number of migraine headache days with acetaminophen/paracetamol use during a 30-day period.
- **Number of days with ergot use** is calculated as the number of days with ergot use during a 30-day period.
- Number of migraine headache days with ergot use is calculated as the number of migraine headache days with ergot use during a 30-day period.

- Number of days with anti-nausea medication use is calculated as the number of days with anti-nausea medication use during a 30-day period.

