- Number of migraine headache days with anti-nausea medication use is calculated as the number of migraine headache days with anti-nausea medication use during a 30-day period.
- Number of days with multiple class medication use is calculated as the number of
 days with multiple class medication use during a 30-day period.
 Multiple class medication use is defined as using at least 2 of the 5 classes (defined
 above) on a day.
- Number of migraine headache days with multiple class medication use is calculated as the number of migraine headache days with multiple class medication use during a 30-day period.
- Number of weekly migraine headache days in Month 1 is calculated as the number of migraine headache days in a 7-day period on which a migraine headache occurs. At month 1, the first 7 calendar days will be counted as week 1, the second 7 calendar days will be counted as week 2, the third 7 calendar days will be counted as week 3, and the rest of days will be counted as week 4.

Combination medications (such as aspirin/acetaminophen/caffeine) will be counted in each medication category that applies (such as NSAIDs/aspirin and Acetaminophen/paracetamol).

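### The SAP's five abortive-medication classes have no place for opioids or barbiturates, which the protocol allows as acute treatment, so the exploratory class-based measures undercount acute medication

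*SAP*

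**What the plan says.** Protocol 6.8, Table CGAI.3, opens with a list headed "Medications allowed for the ACUTE treatment of migraine headaches or other pain or injury". Under that heading, among drugs allowed with restrictions, it has "Opioid and barbiturates no more than 3 days/month (SP II, III and IV", so the allowance covers the prospective baseline, the double-blind phase and the open-label phase. Injectable steroids are also allowed there, as a single emergency dose. Protocol 8.1.1 says that the diary captures the name and dose of acute migraine medication.

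SAP 5.4.1 then states: "Abortive medication use will be classified into the following 5 classes: triptans, nonsteroidal anti-inflammatory drugs (NSAIDs)/aspirin, acetaminophen/paracetamol, ergots, anti-nausea". Three further rules use this list:

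- The average number of classes per migraine day: "Where m_i denotes the number of migraine headache days during a period with i class(es) of abortive medication use, and i = 0,1,...,5". A parallel formula covers all days.
- Multi-class use: "Multiple class medication use is defined as using at least 2 of the 5 classes" on a day.
- Combination products: "Combination medications (such as aspirin/acetaminophen/caffeine) will be counted in each medication category that applies".

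No SAP section says how to score an allowed acute drug that lies outside the five classes.

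The key secondary measure is defined separately and earlier in SAP 5.4.1. It counts days "on which migraine or probable migraine occurs and abortive medication is used", with no mention of class.

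**The concern.** The two documents do not cover the same set of drugs. Because the class index stops at 5 and zero is a defined value, a drug outside the list is not set aside as unclassified. Its day is counted as a day with no class.

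The direction of the error is unhelpful. A patient who replaces a triptan with a plain opioid appears to use fewer classes, and one who adds an opioid to a triptan that is not working appears unchanged. Measures meant to describe how heavily and how variously patients rely on acute medication would miss that escalation.

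At stake are six measures in SAP 5.4.1: the number of classes used (overall and on migraine days), the average number of classes per day and per migraine day, and the number of days and of migraine days with multi-class use. SAP Table CGAI.5.5 has them analysed by MMRM in the double-blind phase and across the double-blind and open-label phases.

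**Working it through.** The plan states no figure to reproduce. The check sets the class list against the permitted list and then applies the SAP's formula.

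**Inputs**
- Classes: 5, with index 0 to 5 (SAP 5.4.1).
- Multi-class threshold: 2 of the 5 (SAP 5.4.1).
- Opioid or barbiturate days: k = 3 per month, the limit in Table CGAI.3, read as applying to the two together.
- Migraine days per month: M = 8 to 30. This range is an assumption. The documents give only the entry minimum of 8 days with migraine features (inclusion criterion 5), and 30 is the ceiling of a 30-day month.

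**Formula**

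Average classes per migraine day = (sum of i × m_i for i = 1 to 5) / (sum of m_i for i = 0 to 5).

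**Case 1: 3 days treated only with a product that has no listed ingredient, one listed class on every other migraine day**

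As written: (0 × 3 + 1 × (M − 3)) / M = 1 − 3/M. With a class for the product: M/M = 1.

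| M | As written | With added class | Difference |
|---|---|---|---|
| 8 | 5/8 = 0.625 | 1.000 | 0.375 |
| 15 | 12/15 = 0.80 | 1.00 | 0.20 |
| 20 | 17/20 = 0.85 | 1.00 | 0.15 |
| 30 | 27/30 = 0.90 | 1.00 | 0.10 |

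**Case 2: 3 days with a triptan plus such a product, one listed class on every other migraine day**

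As written: M/M = 1, with no multi-class days. With the added class: ((M − 3) + 2 × 3) / M = 1 + 3/M, which is 1.375, 1.20, 1.15 and 1.10 at M = 8, 15, 20 and 30, with 3 multi-class days.

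**Case 3: a combination product containing acetaminophen or aspirin**

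The combination rule gives this day one class for the listed ingredient, not zero. The opioid or barbiturate part is still uncounted; with an added class the day would score 2.

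In Cases 1 and 2 the shift is 3/M whatever the other days contain, because each affected day would add one to the numerator and leave the denominator alone. If M falls below 8 on treatment, the shift is larger. For the all-days average over a complete 30-day diary it is 3/30 = 0.10.

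These are effects within one patient-month at the protocol limit. To turn them into effects on arm means would need the proportion of patients using such products and the days of use, by arm. The documents give neither.

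**The case against.** **Use should be low.** Exclusion criterion 30 looks back over half a year and, where its threshold was passed in at least three of those months, removes "Patients who have used opioids or barbiturate containing analgesic >3X per month for the treatment of pain". Criteria 31 and 32 exclude current drugs of abuse and require a negative urine screen or retest. The allowance also covers pain other than headache, which has its own diary question (Q11). This stands as a reason to expect a small effect. It does not make use nil, since the protocol makes explicit provision for it.

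**The affected measures carry no formal claim.** They do not appear in the objectives table, and SAP 5.5.10.3 analyses them without multiplicity adjustment. This stands.

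**Differential use would show elsewhere.** SAP 5.5.9 summarises diary-recorded abortive medication and compares arms in the double-blind phase. This is a partial safeguard, but it does not correct the class measures. The important-deviation rule for opioids and barbiturates looks for more than 7 consecutive days and would not pick up occasional use.

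**The key secondary.** A reader might infer that migraine days with acute medication use are undercounted too. The documents do not support that. The measure refers to any abortive use, diary Q10 asks about any medicine for the headache, and the five-class sentence follows the bullet on the number of classes. The SAP does not spell out that class is irrelevant there, which warrants a clarifying sentence and no more.

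**Anti-nausea drugs.** A reader might also call it an error that these count although the protocol's acute list omits them. Table CGAI.3 does not prohibit them, and counting them is a definitional choice.

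**Conclusion.** The point holds for the class-based measures. The closed list, the index from 0 to 5 and the two-of-five rule together give a wrong count for a drug type that the protocol permits. A day treated only with a product that has no listed ingredient scores zero, and a triptan-plus-opioid day scores as single-class.

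The zero score follows from the formula; the SAP does not state it in words. At the protocol limit, the average number of classes per migraine day is too low by 0.375 at 8 migraine days and by 0.10 at 30, on the assumed range of M and the reading of 3 days for the two drug types together.

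The effect on arm means and on treatment differences is unknown. A biased comparison would require use to differ by arm, and nothing in the documents shows that it does. No primary or key secondary conclusion is shown to depend on this.

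**What to change.** In SAP 5.4.1, add two classes to the list: opioids/barbiturates, and other acute headache medication. One combined class would also do. Extend the index and the multi-class definition to match: 0 to 7 and at least 2 of 7 with two added classes, or 0 to 6 and at least 2 of 6 with one. An opioid/barbiturate class alone would still leave the permitted injectable steroids without a place. One combined class is simpler, but it would score an opioid and a steroid on the same day as a single class.

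State how the combination rule applies to the new classes, in particular whether a minor ingredient such as caffeine triggers the residual class.

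As a clarification only, add a sentence to the definition of migraine days with medication use saying that abortive use there does not depend on class.

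The cost is SAP wording, minor reprogramming and recoding of medication names already collected in the diary. Nothing changes for patients or sites. It is best settled before Interim Analysis #2, which the SAP's revision history describes as the first unblinding of the study team.
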